#### **10.4.2 AEs and SAEs**

AEs will be summarized using Medical Dictionary for Regulatory Activities (MedDRA) System Organ Class and preferred terms. Tables will show by treatment arm (in Part A and Part B) the number and percentage of participants experiencing an AE within a System Organ Class or within preferred term category by severity or by relationship to study product. For the calculations in these tables, a participant with multiple AEs within a category will be counted once under the maximum severity or the strongest recorded causal relationship to study product. Formal statistical testing comparing arms is not planned since interpretation of differences must rely heavily upon clinical judgment.

A listing of SAEs reported to the Division of AIDS (DAIDS) Regulatory Support Center (RSC) Safety Office will provide details of the events including severity, relationship to study product, time between onset and last vaccination, and number of vaccinations received.

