HIV VACCINE
TRIALS NETWORK

PROTOCOL

HVTN 303

A Phase 1, Open-Label Clinical Trial to Evaluate Safety, Tolerability, and Immunogenicity of Adjuvanted HIV-1 Fusion Peptide Conjugate Vaccine (VRC-HIVVCP0108-00-VP) Alone or in Prime-Boost Regimens with Adjuvanted HIV-1 Envelope Trimer 4571 (VRC-HIVRGP096-00-VP) and HIV-1 Trimer 6931 (VRC-HIVRGP0106-00-VP) Vaccines in Healthy Adults

DAIDS DOCUMENT ID 38835

IND 028412 HELD BY DAIDS

CLINICAL TRIAL SPONSORED BY

Division of AIDS (DAIDS)
National Institute of Allergy and Infectious Diseases (NIAID)
National Institutes of Health (NIH)
Department of Health and Human Services (DHHS)
Bethesda, Maryland, USA

STUDY PRODUCTS PROVIDED BY

Vaccine Research Center (VRC)
NIAID, NIH, DHHS
Bethesda, Maryland, USA

September 21, 2023

Final
HVTN 303
Version 2.0

HVTN 303 enrolled (vaccinated) its first participant on August 15, 2022, with the goal to enroll 60 participants in the study. As of Dec 20, 2022, 44 participants were enrolled (no enrollments occurred after this date). Part A (Groups 1, 2, 3, 4, and 5) completed enrollment of 15 participants from August 15 to October 14, 2022.

Part B enrolled 29 participants from November 3 to December 20, 2022: Group 6 enrolled 10 ppts, all of whom received 1 vaccination; Group 7 enrolled 10 participants, 5 of whom received 2 vaccinations; Group 8 enrolled 9 participants, 6 of whom received 2 vaccinations. No participants received a 3rd vaccination.

Over time, the PSRT observed trends in local and systemic reactogenicity (grade 3 fever, grade 3 injection site erythema, and/or induration/swelling), unsolicited adverse events (urticaria, rash, and serum sickness), and temporary increases in absolute eosinophil counts (AECs) post-vaccination. Certain of these events resulted in pauses in all vaccinations, and the PSRT requested the HVTN Safety Monitoring Board (SMB) perform an ad hoc review of all safety data. Following this review on January 11, 2023, the SMB recommended that all vaccinations in the study be permanently discontinued, and that participants be continued in safety follow-up, and these recommendations were implemented.

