6.2.1 Sample size calculations for immunogenicity

The main goals of this trial regarding immunogenicity outcomes involve assessing the ability of FP-conjugate and Trimer 4571 vaccines alone or co-administration to elicit antibody binding FP and envelop trimer antigens and mapping FP-specific serum neutralizing activity induced by the prime vaccines regimens in Groups 5-8 and prime boost vaccines regimens in Groups 7-8. No adjustment for multiple comparisons will be made for the use of multiple assays. The precision with which the true response rate can be estimated from the observed data depends on the true underlying response rate and the sample size. Two-sided 95% CIs for the response rate based on observing a particular rate of responses in the vaccinees is shown in [Table 6-3](#). Calculations are done using the score test method (52). The sample size of n = 13 (Groups 5-6) and n=9 for each of Groups 7 and 8 will be used to evaluate the immunogenicity post the 1st vaccination induced by the vaccination; the sample sizes of n=4, 5 for Groups 7-8 will be used to evaluate the immunogenicity post the 2nd vaccination.

Table 6-3 Two-sided 95% confidence intervals for the true response rate based on observing a particular rate of responses in the vaccinees (n =4, 5, 9, 13)

No. of responses	Observed response rate (%)	95% Confidence interval
2/4	50	[15, 85]
4/4	100	[51, 100]
2/5	40	[11.8, 76.9]
4/5	80	[37.6, 96.4]
3/9	33.3	[12.1, 64.6]
6/9	66.7	[35.4, 87.9]
9/9	100	[70.1, 100]
3/13	23.1	[8.2, 50.3]
6/13	46.2	[23.2, 70.9]
9/13	69.2	[42.4, 87.3]

As shown in [Table 6-4](#), there is limited power for a formal comparison of immunogenicity response rates between Group 7 (n=9) and Group 8 (n=9). For either 80% or 90% power, the sizes of differences that the trial is powered to detect are fairly large. These calculations use a Fisher exact 2-sided test with a type I error rate of 0.05.

Table 6-4 Power for comparison of response rates between 2 arms (n1 = 9, n2 = 9)

True response rate Arm 1 (%)	Minimum true response rate in Arm 2 in order to detect a difference	
	80% power	90% power
10	83	91
20	92	99
30	99	

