## **4 SAFETY OBJECTIVES AND ENDPOINTS**

*Primary objective 1:*

To evaluate the safety and tolerability of the following regimens in healthy adults:

- Adjuvanted FP conjugate vaccine administered IM at a dose of 25 or 200 mcg,
- Adjuvanted Trimer 6931, administered IM at a dose of 100 or 200 mcg,
- Adjuvanted Trimer 4571 administered IM at 200 mcg, or
- Prime-boost vaccination regimens of FP conjugate, Trimer 4571, and Trimer 6931 vaccines.

*Primary endpoint 1:*

Local and systemic reactogenicity signs and symptoms, laboratory measures of safety, and adverse and serious adverse events.

SAEs, medically attended adverse events (MAAEs), adverse events of special interest (AESIs) and AEs leading to early participant withdrawal or permanent discontinuation which will be collected throughout the study and for 12 months following any receipt of study product. Additionally, all adverse events will be collected for 28 days after any receipt of study vaccination. All safety lab related adverse events will be collected throughout duration of study.

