## 10 STATISTICAL ANALYSIS

### 10.1 Statistical analyses

This section describes the final study analyses, unblinded as to treatment arm assignment. All data from enrolled participants will be analyzed according to the initial randomization assignment regardless of how many vaccinations they received. In the rare instance that a participant receives the wrong treatment at a specific vaccination time, the Statistical Analysis Plan (SAP) will address how to analyze the participant's safety data. Analyses are modified intent-to-treat in that individuals who are randomized but not enrolled do not contribute data and hence are excluded. Because of the brief length of time between randomization and enrollment (typically no more than 4 working days), very few such individuals are expected.

Analyses for primary endpoints will be performed using statistical analysis system (SAS) and R. All other descriptive and inferential statistical analyses will be performed using SAS, StatXact, or R statistical software.

No formal multiple comparison adjustments will be employed for multiple safety endpoints, multiple primary immunogenicity endpoints, or secondary endpoints. However, multiplicity adjustments will be made for certain immunogenicity assays, as discussed below, when the assay endpoint is viewed as a collection of hypotheses (eg, testing multiple peptide pools to determine a positive response).

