#### **10.4.1 Reactogenicity**

The number and percentage of participants experiencing each type of reactogenicity sign or symptom will be tabulated by severity and treatment arm in Part A and Part B and the percentages displayed graphically by arm. For a given sign or symptom, each participant's reactogenicity will be counted once under the maximum severity for all injection visits. In addition, to the individual types of events, the maximum severity of local pain or tenderness, induration or erythema, and of systemic symptoms will be calculated. Kruskal-Wallis tests will be used to test for differences in severity across arms and Wilcoxon rank sum test will be used to test for difference in severity between 2 arms in Part B.

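### Safety is summarised only by randomised group, so two product-dose rates that could rest on 13 participants are reported at 3 and 10, and Group 7 yields no first-dose FP conjugate rate

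*SAP*

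**What the plan says.** Primary objective 1 (SAP 4; Protocol 3.1) names products and doses and gives no group numbers. Two of its items are "Adjuvanted FP conjugate vaccine administered IM at a dose of 25 or 200 mcg" and "Adjuvanted Trimer 4571 administered IM at 200 mcg".

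The safety summaries are organised by group:
- General rule (SAP 10.1): "All data from enrolled participants will be analyzed according to the initial randomization assignment regardless of how many vaccinations they received".
- Reactogenicity (SAP 10.4.1): by arm, where "each participant's reactogenicity will be counted once under the maximum severity for all injection visits".
- AEs (SAP 10.4.2): "Tables will show by treatment arm (in Part A and Part B) the number and percentage of participants". A participant with several AEs in a category counts once, at the greatest severity or strongest relationship.

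In SAP 9 an arm is a group of 3, 9 or 10. The only combination considered there is all 44 participants, and only to illustrate precision. The table list in SAP 11.2 has no product-received table.

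On exposure, the boxed summary at the front of the protocol says "Group 6 enrolled 10 ppts, all of whom received 1 vaccination", that 5 of the 10 in Group 7 received two vaccinations, and that nobody received a third. Protocol 7.1 gives Groups 5 and 6 the same Week 0 preparation (200 mcg Trimer 4571 with 20% Adjuplex, 0.8 mL in two syringes). It gives Groups 2 and 7 the same Week 0 preparation of 200 mcg FP conjugate.

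For immunogenicity, Protocol 6.2.1 does combine Groups 5 and 6: "The sample size of n = 13 (Groups 5-6").

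**The concern.** The trial stopped early, after a pattern of grade 3 fever and injection-site reactions, urticaria, rash, serum sickness and eosinophil rises. Its stated primary goal is to identify safety concerns associated with the products, so the natural summary is a rate per product and dose on everyone who received it. SAP version 2.0 was revised to match the post-stop protocol, when the delivered exposures were already known, but it kept the group layout.

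Two things are lost. The first is precision: 13 people with the same exposure appear as 3 and 10. The second matters more. Group 7 mixes five participants with one FP dose and five with two, and the maximum-over-visits rule merges the doses. The only single-dose 200 mcg FP reactogenicity rate in the planned tables then comes from Group 2, with three people, for a product not given to humans before this trial. The once-per-category rule has the same effect on AEs.

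**Working it through.** **Inputs.** Group sizes and doses received come from the protocol's boxed summary. Treatments come from Protocol 7.1. The interval method is the score method (SAP 9).

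**Exposure as delivered**

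| Exposure | Part A | Part B | Total |
|---|---|---|---|
| One dose, 200 mcg Trimer 4571 | Group 5, n=3 | Group 6, n=10 | 13 |
| First dose, 200 mcg FP conjugate | Group 2, n=3 | Group 7, n=10 | 13 |

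**Reproducing the plan.** The rate giving a 90% chance of at least one event is 1 − 0.1^(1/n). This gives 53.6% at n=3, 22.6% at n=9, 20.6% at n=10 and 5.1% at n=44, all as printed in SAP 9. With zero events the score upper bound is z²/(n + z²), with z² = 3.84:
- n=3: 3.84/6.84 = 56.1%, as printed.
- n=9: 3.84/12.84 = 29.9%, as printed.
- n=10: 3.84/13.84 = 27.8%. The plan prints 29.2%, which is not the score value. I use 27.8% throughout.

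The 3/13 interval in Protocol Table 6-3, 8.2% to 50.3%, also reproduces.

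**Precision at n=13.** 3.84/16.84 = 22.8%.

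| | n=3 | n=10 | n=13 |
|---|---|---|---|
| Score upper bound, 0 events | 56.1% | 27.8% | 22.8% |
| Score interval, 1 event | 6.1 to 79.2% | 1.8 to 40.4% | 1.4 to 33.3% |

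**Chance of observing an event.** At a true rate of 10%, the chance that at least one of the 13 has an event is 1 − 0.9^3 × 0.9^10 = 1 − 0.9^13 = 74.6%, whether they sit in one column or two. The figures of 27.1% (n=3) and 65.1% (n=10) describe subsets of the same 13 people. The layout of the tables changes nothing here.

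**Recoverability.** Groups 5 and 6 contain different people, each with one dose and each counted once per category. Their planned counts can be added: x₅ + x₆ over 13. For Groups 2 and 7 this fails. The Group 7 reactogenicity count is a maximum over one dose for five people and over two doses for the other five, so x₂ + x₇ is not a first-dose count.

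**Windows that can be pooled**
- Solicited reactogenicity: 7 days after dose 1 in all groups. Protocol 8.3 states that the extension to 10 days was not implemented.
- Unsolicited AEs: 28 days after each vaccination (Protocol 9.1). In Group 7 the allowable window for dose 2 is Day 28 −6/+7, that is, Days 22 to 35 (Appendix F). A second dose on Days 22 to 27 cuts the 28-day window short.
- Laboratory events: Part A safety laboratory sampling ended 4 weeks after vaccination, while Part B safety follow-up with laboratory sampling ran for at least 7 months. Part A has a Week 4 visit; Group 6 goes from Week 2 to Week 12 (Appendices B and D).
- Serious, medically attended and special-interest AEs are collected for 12 months. Cutting Group 7 at dose 2 leaves about 22 to 35 days for five of its participants, against 52 weeks in Group 2.

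**The case against.** The strongest reply is that little is missing. FP conjugate 25 mcg and Trimer 6931 at 100 and 200 mcg were each given in one group, so the group tables already give those rates. Groups 5 and 6 each estimate the single-dose Trimer 4571 rate and can be summed by hand, and Group 2 estimates the single-dose 200 mcg FP rate. SAP 10.4.2 plans counts and percentages and does not ask for intervals. The gain over n=10 is modest. The pooling precedent in Protocol 6.2.1 covers Groups 5 and 6 only; Group 7 stays on its own at n=9. Pooling also crosses cohorts with unequal follow-up. The serious-AE listing shows the number of vaccinations received, and the Safety Monitoring Board listings cover severe reactogenicity, special-interest, medically attended and related events.

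Most of this stands, and it rules out two stronger readings that a reader might infer. One is that the product-level rates are never estimated. They are, though on small groups. The other is that splitting the groups lowers the chance of seeing an event. It does not, as the working shows. The follow-up objection also stands against pooling all AEs without restriction.

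It does not remove the Group 7 problem. No planned table separates dose 1 from dose 2 there, and a listing of serious or severe events does not supply a first-dose rate for all grades.

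**Conclusion.** The point holds as a limited, inexpensive improvement. Two product-dose exposures named in objective 1 are reported at n=3 and n=10 rather than n=13. The gain in precision is large against the Part A groups (zero-event upper bound 56.1% to 22.8%) and modest against the Part B groups (27.8% to 22.8%). The more substantial loss is the first-dose 200 mcg FP reactogenicity rate, which the planned tables give only from Group 2.

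This rests on three assumptions. The groups match as received; Group 6 was scheduled for further doses, so they do not match as planned. The reported dose counts are final. The Part A and Part B cohorts are similar enough for a descriptive pooled rate, which the documents neither assert nor contradict.

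**What to change.** Keep every by-group table. Add two descriptive product-received columns with score intervals to the reactogenicity and AE tables:
- Groups 5+6 after their single 200 mcg Trimer 4571 dose (n=13).
- Groups 2+7 after dose 1 of 200 mcg FP conjugate (n=13).

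Restrict both to shared windows: 7-day solicited reactogenicity after dose 1, and unsolicited clinical AEs within 28 days of dose 1, censored at any second dose, with the number of truncated windows in a footnote. Note also that Group 6 had no scheduled Week 4 visit. Leave out laboratory-detected AEs, or limit them to laboratory visits common to the pooled groups. Do not pool 12-month percentages of serious, medically attended or special-interest AEs for Groups 2+7.

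The cost is two columns and a dose-1 reactogenicity derivation for Group 7; no new data are needed. The downside is that the columns mix Part A and Part B cohorts that were randomised separately and in sequence. They should be labelled as estimation only and not used to compare arms.

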## SAP Modification History

The version history of, and modifications to, this statistical analysis plan are described below.

SAP Version	Modification
1.0	Initial
2.0	Update the safety SAP based on protocol version 2.0

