### 11.2 List of Tables

The following tables are included in the SMB reports and FSR for Safety:

- Enrollment Report
- Demographics and Study Product Administration Frequencies
- Study Product Administration Errors
- Maximum Local and Systemic Reactogenicity Summaries
- Adverse Events by Treatment – Listed by Body System and Severity – By Decreasing Frequency
- Adverse Events by Preferred Term and Severity – by Decreasing Frequency – Includes Severe, Potentially Life-threatening or Fatal Events only
- Adverse Events by Preferred Term and Severity – by Decreasing Frequency – Includes All Severities
- Adverse Events by Preferred Term and Severity – by Decreasing Frequency – Includes Related Events only
- Adverse Events by Preferred Term and Relationship to Study Product – by Decreasing Frequency – Includes Events of Any Relationship

Additional tables included in the FSR for Safety:

- Social Impact Summary
- End of Study HIV Diagnostic Testing Results (Vaccine-Induced Seropositivity/Reactivity)

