### **11.3 List of Participant Listings**

These participant listings are included in the SMB reports:

- Discontinuation Status
- Severe or Life-Threatening Local and Systemic Reactogenicities
- Moderate, Severe or Life-threatening Erythema / Induration
- Serious Adverse Events (SAEs)/Expedited Adverse Events (EAEs)
- Severe, Life-Threatening, or Fatal Adverse Events
- Adverse Events of Special Interest (AESI)
- Medically Attended Adverse Events (MAAE)
- Study Product Related Events
- Pregnancies
- HIV Infections

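### The final safety report will not give the proportion of participants with any of urticaria, rash or serum sickness, nor split it by dose number, although SAP v2.0 was revised after the vaccinations were stopped

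*SAP*

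**What the plan says.** SAP 10.4.2 (the same plan as Protocol 6.5.3.2) shows, for each arm, "the number and percentage of participants experiencing an AE within a System Organ Class or within preferred term category by severity" or by relationship to product. Its counting rule is that "a participant with multiple AEs within a category will be counted once under the maximum severity or the strongest recorded causal relationship". No between-arm test of AEs is planned, and section 10.4 attaches no interval to any safety percentage.

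The tables in SAP 11.2, for example "Adverse Events by Preferred Term and Relationship to Study Product", follow the same layout and go into both the SMB reports and the final safety report. None combines preferred terms and none is split by dose number.

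For SAEs only, 10.4.2 promises a listing with "time between onset and last vaccination, and number of vaccinations received". SAP 11.3 also names listings of product-related events, AESIs, MAAEs and severe AEs, but describes no columns and introduces them with "These participant listings are included in the SMB reports". The neighbouring lists of tables and figures name the final report as well.

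The Protocol's version 2.0 summary says that the safety review team saw trends in grade 3 fever and grade 3 injection-site reactions, in "unsolicited adverse events (urticaria, rash, and serum sickness), and temporary increases in absolute eosinophil counts (AECs) post-vaccination". Pauses, an ad hoc SMB review and permanent discontinuation followed. The SAP's modification history describes version 2.0 as "Update the safety SAP based on protocol version 2.0", so it was written with that known.

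**The concern.** The stated primary goal is to identify safety concerns associated with the products (SAP section 5). Once a group of unsolicited reactions has been named among the trends before a stop, a reader of the final report will ask three things: how many recipients had any of them, after which dose, and how precisely that is known. The planned layout answers these only in part.

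Counting once per category removes duplicates within a preferred term, not between terms, so the separate rows cannot be added. Arms are also not the same as exposures. Groups 7 and 8 each mix one-dose and two-dose recipients, while identical first doses are split across arms: 200 mcg FP conjugate in Groups 2 and 7, and 200 mcg Trimer 4571 in Groups 5 and 6. The Protocol already uses n = 13 for Groups 5-6 in its immunogenicity precision calculation (6.2.1). Safety has no counterpart.

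**Working it through.** **1. The plan's own intervals.** SAP Table 6-2 says that its intervals use the score method. With p = k/n and z = 1.96, the score limits are [p + z²/2n ± z·√(p(1−p)/n + z²/4n²)] / (1 + z²/n).

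- The n = 3 and n = 9 rows reproduce, for example 1/9: 2.0 to 43.5.
- The n = 10 and n = 44 rows do not. For 2/10: (0.2 + 0.1921 ± 1.96·√(0.016 + 0.0096)) / 1.3841 = (0.3921 ± 0.3136) / 1.3841, which is 5.7% to 51.0%.

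| Observed | Table 6-2 (%) | Score interval (%) |
|---|---|---|
| 0/10 | 0 to 29.2 | 0 to 27.8 |
| 1/10 | 0.1 to 30.5 | 1.8 to 40.4 |
| 2/10 | 0.2 to 31.9 | 5.7 to 51.0 |
| 0/44 | 0.1 to 9.8 | 0 to 8.0 |
| 1/44 | 0.3 to 11.4 | 0.4 to 11.8 |
| 2/44 | 0.6 to 12.9 | 1.3 to 15.1 |

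The Agresti-Coull, Clopper-Pearson, Jeffreys and Wald methods do not match those rows either. The point made here does not rest on them, but they should not be used to read any observed rate.

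**2. Exposure** (Protocol version 2.0 summary and section 2.6). Two doses: 5 of 10 in Group 7 and 6 of 9 in Group 8, so 11 participants. One dose: 44 − 11 = 33. Doses given: 33 × 1 + 11 × 2 = 55, that is 44 first and 11 second doses. Identical first doses: Groups 2 + 7 = 3 + 10 = 13, and Groups 5 + 6 = 3 + 10 = 13.

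**3. What separate rows leave open.** If a, b and c participants have urticaria, rash and serum sickness, the number with any of them lies between max(a, b, c) and a + b + c. The documents give no counts for this trial. The only figure is one serum sickness event after Adjuplex-adjuvanted vaccines (Protocol 2.11.2). The counts below are assumptions.

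| Assumed counts | Denominator | Lower bound (95% score CI) | Upper bound (95% score CI) |
|---|---|---|---|
| 2, 1, 1 | 10 (one arm) | 2 = 20% (5.7 to 51.0) | 4 = 40% (16.8 to 68.7) |
| 2, 2, 1 | 44 | 2 = 4.5% (1.3 to 15.1) | 5 = 11.4% (5.0 to 24.0) |
| 3, 3, 1 | 44 | 3 = 6.8% (2.3 to 18.2) | 7 = 15.9% (7.9 to 29.4) |
| 4, 3, 1 | 44 | 4 = 9.1% (3.6 to 21.2) | 8 = 18.2% (9.5 to 32.0) |

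**4. Precision of the added table.** For a pooled first-dose set of 13, 1/13 = 7.7% (1.4 to 33.3) and 3/13 = 23.1% (8.2 to 50.3); the latter agrees with Protocol Table 6-3. For the 11 second doses, 0/11 has an upper limit of 25.9%, and 2/11 = 18.2% (5.1 to 47.7). These intervals describe; they do not discriminate between arms.

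**The case against.** Much of the information is already planned, and that part of the objection stands. Each preferred term gets a rate by arm, severity and relatedness. The organ-class row counts a participant once, so where the terms share a class the overlap is resolved, although that row may also hold other events. SAP 10.4.3 covers laboratory values by arm and visit, with changes from baseline and graded counts, but does not link them to the skin reactions. Dose number is an open question only in Groups 7 and 8, because the other six arms had a single dose. The SMB listings may carry onset and dose, since undescribed columns are not proof of absence. Updates to the AESI list sit in the Study Specific Procedures, which are not among these documents, so a grouped definition there cannot be excluded; the examples in Appendix M name none of the three events.

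A reader might go further and infer that these events form one reaction pattern that ended the trial. The documents do not say so. The version 2.0 summary lists them beside fever, local reactions and eosinophil increases, says only that certain of these events caused pauses, and describes the SMB as reviewing all safety data. A reader might also infer that the rates of these reactions are never estimated. That is true only of the combined proportion.

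What survives is narrow. No planned output for the final report gives the combined count, splits it by dose number or attaches an interval, and a case listing made for the SMB would not be a rate.

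**Conclusion.** The point holds as a gap in the final safety report, and closing it is a cheap improvement. The AE tables in SAP v2.0 are by organ class or preferred term and by randomised arm, without intervals. The proportion with any of urticaria, rash or serum sickness is left bounded rather than stated, and first-dose and second-dose experience are mixed in Groups 7 and 8 (19 participants, 11 with two doses). Under the assumed counts in the working, the uncertainty from overlap alone is about 7 to 9 percentage points of 44, or 20 points in an arm of 10. The true size is unknown because the documents give no counts, and it is zero if no participant had more than one of the three events and the report says so. Grouping the three terms is an analytic choice made after the stop, not a syndrome that the documents define.

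**What to change.** Add to SAP 10.4.2 and 11.2 one descriptive table, labelled as defined after vaccinations were stopped:

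- **Event:** participants with any of a listed set of preferred terms for urticaria, rash or serum sickness, with onset within the 28-day AE collection window after a dose. The second dose falls at day 28, with an allowable window of −6 to +7 days, so state that an event is assigned to the most recent dose.
- **Rows:** by product and dose received, pooling the identical first doses in Groups 2 + 7 and 5 + 6, and by dose number (44 first, 11 second).
- **Interval:** two-sided 95% score intervals computed afresh, not copied from Table 6-2. Correct the n = 10 and n = 44 rows of that table at the same time.

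Add to the final report a listing of these events with onset since last vaccination, doses received, relatedness, and baseline and peak post-dose eosinophil count. Baseline is needed because inclusion criterion 11 admits an out-of-range differential judged not clinically significant.

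The cost is one table and one listing from data already collected. The downsides are that the term list is post hoc and the intervals are wide. No between-arm test should be attached.
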